Figure 7: (a, top left) Length of ventilation (days) is higher in children with flow undershoot forms of PVA when spontaneous breathing does not occur until after the 3rd day of ventilation (b, top right) Diaphragm hypertrophy may be more likely to occur in children with flow-undershoot forms of PVA (c, bottom left) Delirium scores are higher in children with high rates of Double Cycled breaths. (d, bottom right) Reverse Trigger patients receive higher doses of opioids.

Methods and Analysis Hypothesis A: Here we seek to test whether the REDvent intervention results in different rates and subtypes of PVA than usual care. This type of analysis is perfectly suited to secondary analysis of a randomized trial, where the intervention is striving to promote more spontaneous breathing with a downstream influence on PVA. This would not be possible to do with an observational cohort, because of inherent selection bias in which patients are permitted to have more spontaneous breathing. We believe the forms of asynchrony which lead to DC breaths (flow undershoot/premature cycling) and reverse trigger may be different in REDvent versus control patients. This aim will use all available patients with spontaneous breathing in the REDvent dataset (expected 235). For each patient day with spontaneous breathing, PVA subtypes will be analyzed. The proportion of breaths which fall into a particular PVA subtype will be expressed in addition to global asynchrony index, calculated as the total number of asynchronous breaths over the total number of breaths.³⁰ Because rates of PVA may vary from day to day, analysis will focus on both an area under the curve of PVA over all days (calculated as the total number of asynchronous breaths over the total number of breaths available for analysis) in addition

to the highest rate of PVA on any day for each patient, by PVA subtype. PVA and PVA subtype rates per patient will be expressed as a continuous variable and compared between REDvent and usual care patients using a Mann Whitney U test given it is not expected to be normally distributed. PVA subtypes which are different between REDvent and control patients will be considered for mediation analysis (below).

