The REDvent study will evaluate whether the REDvent intervention results in improvement in length of mechanical ventilation (clinical outcome), as well as mechanistic outcomes (PiMax and Diaphragm Atrophy). The impact of REDvent group on time to event variables (i.e. length of ventilation) will be analyzed with competing risk regression (competing risk of death), continuous outcomes (i.e. PiMax) with linear regression, and dichotomous variables (i.e. mortality) with logistic regression. In mediation analysis we will add the PVA subtypes which are different between REDvent and control patients to multivariable models. The PVA subtype will be considered a mediator if it changes the parameter estimate of the REDvent intervention by more than 20%. If the PVA subtype significantly strengthens the association between REDvent intervention and outcomes, then therapeutic trials which seek to decrease that PVA subtype may be beneficial (e.g Reverse Trigger). In contrast, if controlling for PVA subtype weakens the association between REDvent and outcome, then strategies to mitigate that type of PVA may be more harmful (e.g. Flow Undershoot). This approach allows us to simultaneously evaluate the potential benefits of a lung and diaphragm protective strategy and understand the extent to which PVA subtypes which are different between intervention and control groups affects outcomes. This type of causal inference analysis is possible because of the randomized nature of the REDvent trial in which the intervention is likely to affect PVA rates and subtypes.

Sample Size and Power: We anticipate 235 patients available for analysis, with a median time from first day of spontaneous breathing to extubation of 4 days. Using a proposed mediation analysis with a conservative estimate for a partial “r” of 0.3 of the PVA variable with the mediator outcome, a partial “r” of 0.3 for the mediator outcome with the clinical variable, then we would have a power of 0.84 to detect the overall effect estimate in the mediation model.

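### The 20% change-in-coefficient rule for naming an asynchrony subtype a mediator has no error control, and false calls become common where REDvent's total effect is small

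*Combined protocol and SAP*

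**What the plan says.** The 2023 protocol, section H, Specific Aim 2, Hypothesis A, works in two steps. Each subtype's rate is "compared between REDvent and usual care patients using a Mann Whitney U test", and "PVA subtypes which are different between REDvent and control patients will be considered for mediation analysis". No alpha is stated for this screen. The outcome models are competing-risk regression for length of ventilation, linear regression for continuous outcomes such as PiMax, and logistic regression for binary outcomes such as mortality. The plan then adds "PVA subtypes which are different between REDvent and control patients to multivariable models" and applies the rule: "The PVA subtype will be considered a mediator if it changes the parameter estimate of the REDvent intervention by more than 20" per cent, in either direction.

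The text reads a strengthened REDvent association as a sign that trials reducing that subtype may help, and a weakened one as a sign that reducing it may harm. It says randomisation makes this causal inference possible.

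The sample-size paragraph assumes 235 patients and a partial r of 0.3 on each of two links, and quotes "a power of 0.84 to detect the overall effect estimate in the mediation model". It names no test or alpha. Confounders (age, co-morbidities, severity of initial lung injury, diagnosis, medications) are listed under Hypothesis B, not Hypothesis A.

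**The concern.** Mediation needs two links: REDvent must change the asynchrony, and the asynchrony must change the outcome. The Mann-Whitney screen addresses the first. Nothing under Hypothesis A tests the second. A percentage change in a coefficient is itself an estimate, and its denominator is the estimated total effect. When that effect is small, sampling noise alone moves the coefficient by more than a fifth.

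Randomisation protects the comparison of arms on asynchrony and on outcome. It does not protect the link from asynchrony to outcome, so a shared cause such as severity can move the coefficient without any mediation.

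What is at stake is the direction of later work. An inert subtype can be flagged with either sign, and so be read as a target to reduce or as one to leave alone.

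**Working it through.** **The plan's own figure.** With r = 0.3 on both links and N = 235, each link has t = 0.3 × √232 / √(1 − 0.09) = 4.79. The Sobel statistic is 4.79/√2 = 3.39, with two-sided 0.05 power Φ(3.39 − 1.96) = 0.92. For joint significance, atanh(0.3) × √232 = 4.71, so power is Φ(4.71 − 1.96)² = 0.99. The stated 0.84 is not reproduced on these inputs, and the 20% rule is not a test to which a power could refer. That is a separate matter and does not change what follows.

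**Inputs for the rule.** N = 235 comes from section H; 1:1 allocation (118/117) from the SAP. The assumptions are a screen at two-sided 0.05, a subtype differing by d = 0.6 SD between arms, and no effect of the subtype on outcome. On the correlation scale, d = 0.6 is r = 0.3/√1.09 = 0.29, close to the plan's 0.3. The plan's 0.3, however, describes the links "of 0.3 of the PVA variable with the mediator outcome" and "of 0.3 for the mediator outcome with the clinical variable", not REDvent to asynchrony.

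**Algebra (linear model).** The coefficient change equals â·b̂, where â is the arm difference in asynchrony and b̂ the asynchrony–outcome slope. In residual-SD units the standard error is about 1/√N for b̂ and 2/√N for the total effect ĉ. The rule |â·b̂| > 0.2|ĉ| becomes

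(d/2)·|y| > 0.2·|x|, with y ~ N(0, 1), x ~ N(Z, 1), Z = (total effect in SD) × √N/2.

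At Z = 0 the probability is (2/π)·arctan(0.3/0.2) = 0.63.

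**Simulation, with the Mann-Whitney screen** (passed in about 99% of studies):

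| Total effect (SD) | Z | False mediator, 20% rule |
|---|---|---|
| 0.4 | 3.07 | about 10% |
| 0.3 | 2.30 | about 20% |
| 0.2 | 1.53 | about 37% |
| 0 | 0 | about 61% |

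Testing the asynchrony–outcome slope at 0.05 as well gives about 5% in every row.

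**Placing these on the trial's own scale** (false calls per subtype among those passing the screen, for arm separation r = 0.2 and r = 0.3):

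- *Design effects.* A stated power of 0.8 for HR 1.4 implies Z = 1.96 + 0.84 = 2.80; 0.9 for HR 1.5 implies 1.96 + 1.28 = 3.24. The rates are 6% and 14% at 2.80, and 4% and 9% at 3.24.
- *Pilot effect on length of ventilation.* p = 0.36 with 19 versus 90 patients is z = 0.915. Scaled by √[(118×117/235)/(19×90/109)] = √(58.75/15.69) = 1.94, Z = 1.77. The rates are 21% and 32%.
- *Mortality.* The final SAP (Table 1, ventilator-free days row) expects no treatment effect on death. With 12% mortality assumed in both arms, the logistic model gives 53% and 62%.

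**Several subtypes.** If four inert, independent subtypes each differ by r = 0.3, at least one is flagged in 92% of studies at Z = 0, 37% at 2.80 and 25% at 3.24.

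**Confounding.** Let a severity factor correlate 0.4 with both asynchrony and outcome within arms (assumed), with a total effect of 0.3 SD. The 20% rule flags the inert subtype in about 75% of studies unadjusted and about 20% adjusted. Joint significance of both links gives about 69% unadjusted and about 5% adjusted. A better test alone is therefore not enough.

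**The case against.** The strongest reply is that the rule misbehaves mainly where there is little to mediate. The text speaks of strengthening or weakening an association between REDvent and outcome, which presupposes one. A false flag together with a significant total effect occurred in only 5.1%, 4.3%, 3.2% and 0.6% of simulated studies at 0.4, 0.3, 0.2 and 0 SD. This stands as a limit on size, but the plan does not make a significant total effect a condition and names mortality among the outcomes.

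Second, adjustment is not ignored. Hypothesis B lists severity and other confounders, section H speaks of controlling for time to spontaneous breathing, and the SAP adjusts trial analyses for strata and imbalanced baseline variables. Hypothesis B would also examine an inert subtype's link to outcome. This stands too: the fair criticism is that Hypothesis A does not name its covariates and does not make the Hypothesis B result a condition for the mediator label. Adjusting only for variables imbalanced between arms does not help, since a balanced severity factor can still confound asynchrony and outcome.

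Third, section H says the work will mainly establish associations, and its remarks on future trials are hedged. That lowers the stakes but leaves the rule uncontrolled.

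A reader might also infer that non-collapsibility of odds and subdistribution hazard ratios inflates these false calls. The evidence does not support that. Non-collapsibility moves a coefficient only if the added variable is related to outcome given treatment, which an inert subtype is not. The null logistic rate at r = 0.3 (62%) matches the linear one (63%).

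**Conclusion.** The concern holds in conditional form. The absence of error control is plain from the text: across the settings run without confounding (r 0.2–0.4), the false-mediator rate per subtype ranged from about 4% to 72%, and nothing in the plan caps it. It is low to moderate (about 4–14% for r = 0.2–0.3) near the design effects, roughly one in five to one in three at the scaled pilot effect, and above one half where the total effect is nil.

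Two stronger readings should be resisted. One is that the rule often names inert subtypes whatever the setting; near the design effects it does not. The other is that about three quarters of such calls would be false through confounding; that figure is the chance of flagging one inert subtype at a total effect of 0.3 SD with severity left unadjusted, and it falls to about 20% on adjustment.

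The sizes rest on the assumed arm difference, screening alpha and severity correlations, approximately normal asynchrony measures on the modelling scale and, for the four-subtype figures, independence. No primary or safety conclusion depends on this analysis.

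**What to change.** - Replace the 20% rule with the estimated indirect effect and a bootstrap 95% interval, and call a subtype a mediator only if the interval excludes 0. Joint significance of both links is an acceptable alternative: with both at r = 0.3 its power is 0.99.
- State the covariates of the Hypothesis A models: the randomisation strata and the baseline confounders already listed for Hypothesis B (age, co-morbidities, severity of initial lung injury, diagnosis).
- Apply Holm across subtypes, with interval levels to match. Four independent null subtypes at 0.05 each give 1 − 0.95⁴ = 18.5% familywise.
- For length of ventilation, estimate the indirect effect on an absolute scale, for example the difference in cumulative incidence of extubation, not as a difference of subdistribution hazard coefficients.
- Describe every result as conditional on no unmeasured confounding between asynchrony and outcome.

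The cost is fewer subtypes called mediators and somewhat more analysis work for the competing-risk outcome. The covariates are already planned for Hypothesis B, so no new data are needed.

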when evaluating for readiness for ventilator liberation.²¹ These patients may have lower rates of PVA because they are not permitted to breathe spontaneously until the ARDS is largely resolved, but they may have longer length of ventilation because of the lack of spontaneous breathing. A balanced lung and diaphragm protective strategy, like what is being tested in the REDvent trial, promotes spontaneous breathing earlier during ventilation. We hypothesize that this will result in shorter time on ventilation by reducing the rates of over and under assistance myotrauma (VIDD) as well as more lung protection (VILI).^{22,24,45} However, earlier spontaneous breathing may result in a higher overall rate of PVA in REDvent versus control patients, but a different distribution of PVA subtypes. Because REDvent targets physiologic levels of respiratory effort, it is likely that the under-assistance related causes of PVA which lead to double cycling (flow undershoot/premature termination) will occur less frequently. However, the lung protective component of REDvent frequently uses a higher ventilator rate than usual care, which may make Reverse Trigger more common, with double cycling. **It is therefore highly plausible that PVA frequency and subtype may mediate the relationship between REDvent intervention and outcome (Figure 5).** It is therefore important to understand when the benefits of spontaneous breathing related to prevention of diaphragm atrophy are outweighed by any additional risks related to PVA. The analytic framework must consider these potentially competing principles. Adult data confirms associations between PVA (and its subtypes) and adverse clinical outcomes.¹²⁻¹⁶ Nevertheless, human studies have not confirmed mechanistic pathways involved, although pre-clinical data support these proposed mechanisms of injury.⁶⁴⁻⁶⁷ While this study will primarily establish associations, a mediation approach (see below) to the analysis allows for causal inference and specifically leverages the **randomized** nature of the REDvent trial. To decouple these effects, when analyzing the relationship between PVA variables and length of ventilation, we stratify or control for the time to spontaneous breathing.

[figure not shown]

Figure 6: Relationship between Asynchrony index and sarcomere disruption of the diaphragm in a rabbit model for PVA

sarcomere disruption and atrophy result in functional impairments seen in VIDD, albeit with different mechanisms.

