Preclinical data confirms that PVA leads to VIDD and VILI. Several mechanistic studies, including published analysis by our group, confirms that PVA leads to VIDD and VILI.⁶⁴⁻⁶⁷ In a rabbit model, we identified that VIDD was reduced with a ventilation strategy promoting spontaneous breathing using pressure support ventilation compared to controlled ventilation, but that this injury could be further reduced with Neutrally Adjusted Ventilatory Assist (NAVA) by reducing the rates of PVA.⁶⁷ Interestingly, diaphragmatic injury from over-assistance myotrauma (common during controlled ventilation without spontaneous breathing) resulted in atrophy, while diaphragmatic injury from PVA was mediated by sarcomere disruption. There was a dose response relationship between Asynchrony Index and fraction of sarcomere disruptions in the diaphragm (Figure 6). Both

PVA subtypes are associated with clinical and mechanistic outcomes. Preliminary analysis from 65 patients in the REDvent dataset evaluated the association between PVA rates on the first day of spontaneous breathing and outcomes. While the sample size from this preliminary data is under-powered, it highlights the potential magnitude of effect we may see with the larger sample size in this application. We have not conducted group-based comparison (REDvent versus control), as study investigators need to remain blinded to group-based analyses until completion of REDvent (Dec 2023). Flow undershoot represents inadequate support on the ventilator and not surprisingly was associated with longer length of ventilation ($p < 0.05$, Figure 7a) perhaps through hypertrophy of the diaphragm (Dte increased), although this analysis is limited by sample size with only 7/65 patients in the hypertrophy group ($p = 0.4$, Figure 7b). Moreover, patients who had DC breaths had higher rates of delirium, as measured by the Cornell Assessment of Pediatric Delirium (CAPD) screener ($p < 0.01$, Figure 7c). This may relate to agitation from PVA which manifests with the same symptoms as delirium, or it may be that delirium itself makes it harder for patients to synchronize with the ventilator. Children with reverse trigger received higher doses of opioids ($p < 0.01$, Figure 7d), which re-enforces that alteration of neural respiratory rate (suppressed with opioids) may make RT more common.

[figure not shown]

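### The direction in which the REDvent coefficient moves on adjustment cannot show whether reducing an asynchrony subtype helps or harms; for flow undershoot the stated reading is backwards on the protocol's own expected signs

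*Combined protocol and SAP*

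**What the plan says.** The rule is in the current protocol, Section H, Specific Aim 2, under Methods and Analysis Hypothesis A. Subtypes whose rates differ between arms enter the multivariable outcome models. "The PVA subtype will be considered a mediator if it changes the parameter estimate of the REDvent intervention by more than 20" per cent. Two interpretive sentences follow.

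- If adjustment strengthens the REDvent association, "then therapeutic trials which seek to decrease that PVA subtype may be beneficial (e.g Reverse Trigger").
- By contrast, "if controlling for PVA subtype weakens the association between REDvent and outcome, then strategies to mitigate that type of PVA may be more harmful"; the example given is flow undershoot.

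Neither sentence sets a condition on whether REDvent raises or lowers the subtype, or on whether the subtype goes with better or worse outcome.

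Elsewhere the same aim indicates what it expects for these quantities.

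- REDvent and ventilation time (Preliminary Data): "We hypothesize that this will result in shorter time on ventilation".
- REDvent and flow undershoot (Preliminary Data): "it is likely that the under-assistance related causes of PVA which lead to double cycling (flow undershoot/premature termination) will occur less frequently".
- Flow undershoot and outcome (Preliminary Data): "Flow undershoot represents inadequate support on the ventilator and not surprisingly was associated with longer length of ventilation", with p < 0.05 in 65 patients. Table 2 of Section H also places inadequate-support asynchrony on the lung-injury and over-use diaphragm-injury pathways.
- REDvent and reverse trigger (Preliminary Data): it may become more common, because REDvent often uses a higher ventilator rate.

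**The concern.** A treatment coefficient weakens on adjustment when part of the treatment's effect runs through the added variable. That alone does not say whether the variable is good or bad for the patient. One also needs to know which way treatment moves it. The plan omits that step and gives weakening a fixed meaning.

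The named example shows the consequence. If flow undershoot behaves as the protocol expects, weakening is the result to look for, and it would support reducing flow undershoot. The rule tells the analyst to read it as a caution against doing so. The aim is meant to inform later therapeutic trials, and flow undershoot was the commonest subtype in the REDvent preliminary cohort, at 13.8% of breaths. A reversed reading could steer those trials away from a target that the protocol treats as injurious.

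**Working it through.** The plan attaches no figure to this rule, so there is none to reproduce. The power of 0.84 in the following paragraph concerns detection of a mediated effect and plays no part here.

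**Formula.** In linear mediation, c = c′ + a·b, so c′ = c − a·b. Here c is the total REDvent effect on length of ventilation, c′ the effect adjusted for the subtype, a the effect of REDvent on the subtype, and b the effect of the subtype on length of ventilation given arm. Lowering the subtype by one unit changes length of ventilation by −b. Negative values of c mean benefit.

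**Inputs.** Only the signs come from the documents. For flow undershoot they are c < 0, a < 0 and b > 0. The magnitudes c = −1.0, |a| = 0.5 and |b| = 0.6 are assumptions for illustration.

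| Row | REDvent and the subtype | Subtype and ventilation | a·b | c′ | Change in size | −b | Lowering the subtype | Plan's reading |
|---|---|---|---|---|---|---|---|---|
| 1 (flow undershoot as expected) | lowers, a = −0.5 | lengthens, b = +0.6 | −0.3 | −0.7 | weakens 30% | −0.6 | may help | may harm |
| 2 (reverse trigger as expected) | raises, a = +0.5 | lengthens, b = +0.6 | +0.3 | −1.3 | strengthens 30% | −0.6 | may help | may help |
| 3 | raises, a = +0.5 | shortens, b = −0.6 | −0.3 | −0.7 | weakens 30% | +0.6 | may harm | may harm |
| 4 | lowers, a = −0.5 | shortens, b = −0.6 | +0.3 | −1.3 | strengthens 30% | +0.6 | may harm | may help |

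Least squares on 200,000 simulated patients gave −30.3%, +30.2% and −30.1% for rows 1 to 3.

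Rows 1 and 3 give the same weakening, past the 20% threshold, with opposite implications. Rows 2 and 4 do the same for strengthening. With a beneficial total effect, the plan's reading is right in rows 2 and 3, where REDvent raises the subtype, and wrong in rows 1 and 4, where REDvent lowers it. The rule therefore assumes, without saying so, that REDvent raises the subtype. That matches the expectation for reverse trigger but not for flow undershoot.

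**Sensitivity to the assumed sizes.** With another set for row 1 (c′ = −0.10, a = −0.6, b = 0.4), a·b = −0.24 and c = −0.10 − 0.24 = −0.34. The coefficient weakens by 0.24/0.34, about 71%. The percentage follows the assumptions. The direction does not, as long as |a·b| is below 2|c|; beyond that the adjusted effect has the opposite sign and is the larger in size.

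**Condition on the total effect.** If REDvent's total effect were adverse, the pattern would change. With c = +1.0, a = −0.5 and b = −0.6, a·b = +0.3 and c′ = +0.7. The coefficient again weakens, and lowering the subtype may harm. The direction of change cannot be read without the sign of c either.

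**The case against.** The strongest defence is that both paths are already planned. Hypothesis A compares each subtype's rate between arms, and Hypothesis B models each subtype against length of ventilation with confounders. The investigators will therefore have both signs in hand. This stands as far as it goes, and it makes the repair cheap. But the interpretive sentences use neither result, so the two analyses could point in opposite directions on one subtype with nothing to reconcile them.

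Second, the wording is hedged and concerns strategies, not the asynchrony itself. Section H notes under Aim 1 that the responses to flow undershoot include more support or suppressing drive, and under Aim 3 that removing one asynchrony may over-assist the patient. A strategy can harm even when its target is harmful. That trade-off is real, but weakening of the REDvent coefficient does not measure it.

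Third, the signs for flow undershoot are not established. Hypothesis (a) predicts only a different distribution of subtypes, and earlier spontaneous breathing may raise the overall asynchrony rate. The harm data come from 65 patients in an analysis the protocol itself calls under-powered, pooled because no comparison by arm was made. The Figure 7 caption narrows it further: "Length of ventilation (days) is higher in children with flow undershoot forms of PVA when spontaneous breathing does not occur until after the 3rd day". All of this stands. It is a reason to let interpretation depend on the estimated signs.

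A reader might infer that weakening never signals harm from mitigation, or that the analysis is bound to give wrong advice on flow undershoot. The documents support neither. Row 3 is possible, for instance if a subtype marks beneficial spontaneous breathing, and the flow-undershoot signs may turn out otherwise.

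**Conclusion.** The rule is wrong as written. The direction of change in the REDvent coefficient does not identify whether reducing a subtype helps or harms. For flow undershoot, the protocol's own expected and preliminary signs make the stated reading backwards.

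The conclusion on flow undershoot rests on three assumptions: REDvent's total effect is beneficial, REDvent lowers flow undershoot, and flow undershoot lengthens ventilation. The general point needs none of them, because opposite situations give the same movement. The identity is exact for linear models. Competing-risk and logistic models, which the plan also uses, change the size of the shift but do not supply the missing signs.

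No size can be given from the documents. It would be tempting to quote 30% or 71% as the expected attenuation, but both come from assumed inputs. The issue is confined to the ancillary asynchrony analysis and does not touch the trial's primary result.

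**What to change.** Replace the two interpretive sentences under Hypothesis A of Aim 2 with text to this effect:

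- For each subtype, report the REDvent-to-PVA effect, the PVA-to-outcome effect given arm and the confounders listed under Hypothesis B (demographics and co-morbidity, initial lung-injury severity, diagnosis, medications), and the indirect effect with a confidence interval.
- Base any statement on whether lowering a subtype may help or harm on the sign of the adjusted PVA-to-outcome path, not on whether the REDvent coefficient strengthens or weakens. State the sign convention for each model, since in a time-to-extubation model benefit appears as a higher rate of extubation.
- State that asynchrony is not randomized, so this path can be confounded or run in reverse, and the reading is hypothesis-generating. The protocol already raises reverse causation for delirium.

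The 20% criterion may stay as a description of size. The cost is two rewritten sentences, study arm as a covariate in the Hypothesis B models, and an interval for the indirect effect. No new data are needed.
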